effective treatment for depression in younger [Krogh et al., 2011] and older adults [Blake et al., 2009]. Importantly, exercise also addresses vascular risk factors thought to be particularly relevant to aging (Blaha et al., 2016), in general, as well as depression in late life [Alexopoulos et al., 2006, Sheline et al., 2010]. While there have been several studies demonstrating the benefits of exercise on depression in older adults, no known study has examined the positive benefits of a structured, group exercise program on mood and well-being in an aging sample. As an ancillary aim, we will also examine the impact of a structured exercise intervention on cognitive functioning. Fit and Strong!, a physical activity / behavior change program for older adults with lower extremity osteoarthritis, has demonstrated efficacy, effectiveness, and ease of dissemination for individuals with osteoarthritis living in the community [Hughes et al., 2004, 2006, 2010]. The goal of this study is to adapt Fit & Strong! for increasing positive affect and reducing negative affect and depressive symptoms among older adults residing in the community.

C. Research Design and Methods

C.1 General study design

We will enroll 40 subjects in this study between the ages of 60 and older, from the community who score at least 1 on the Patient Health Questionnaire-8 (PHQ). Up to 20 participants will have PHQ-8 scores of 1-4, while up to one-half of participants will have PHQ scores >4. At the outset of the study, up to 20 individuals will be randomly assigned to the intervention portion of the study, while up to 20 individuals will be randomly assigned to a crossover wait-list group, who will undergo the intervention beginning at study week 10. Outcome measures will be administered to all participants before the intervention and to the intervention group after they undergo the intervention. The wait-list group will complete all of their outcome measures before they begin the intervention(see Figure 1).

Figure 1

C.2 Phone screen and Study Visits

C2.1 Pre-Study Screen:

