Before being scheduled to a study visit, potential participants will undergo a phone or in-person screen where the aims and structure of the study will be explained to them. The potential participants will be allowed to ask specifics about the study and express their interest in the study. If they wish to participate in the study, they will undergo a phone screen assessing past and current medical and psychiatric history, as well as answer a six-item screener, Patient Health Questionnaire-8 and Physical Readiness Questionnaire. Participants will also be informed about compensation during the phone screen. If a participant scores 10 or higher on the PHQ, but refuses to participate in the study, we will refer them to a list of treatment facilities including UIC's Psychiatry Outpatient Program. Scores above 10 or 11 are thought to be indicative of clinical depression (see <https://www.ncbi.nlm.nih.gov/pubmed/18752852> or <https://www.ncbi.nlm.nih.gov/pmc/articles/PMC2943487/>) Participants who express interest and are eligible for the intervention group will also be screened with the MRI Screening document to see if they are eligible for the optional MRI component of the study.

C2.2. Study Enrollment and Pre-Intervention Measures (approximately 3 hours)

All eligible individuals will be invited to the University of Illinois at Chicago or to Oakwood Shores for their first study visit, which will last approximately two hours. First, the entire study will be described to participants and any questions that they have about the study will be answered. After the participant has signed the consent form, they will participate in an interview with a trained research assistant. Some of these questions will be of a personal nature and may make the participant feel uncomfortable. They can decline to answer any question. Next, they will complete a packet of self-report questionnaires and will undergo a neuropsychological (memory/cognitive) testing battery and mobility assessment with a trained staff person. Randomized participants of the intervention group will be invited to participate in optional MRI testing which will take place pre-intervention (Week 0) and post-intervention (Week 9).

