If a truly unanticipated result and compelling reason to attempt to inform subjects becomes evident - either for an individual or for a group, we will submit a request to the University of Illinois IRB to send a letter to ALL subjects enrolled in the study stating that information may be available with a phone number and have a trained person available to answer questions. However, we don't anticipate any such results. Decisions regarding when something is of importance will be made by the study investigators in consultation with a genetic counselor. Study participants will not be responsible for the costs of genetic counseling incurred because of this study.

As with any exercise program, there is always a risk of injury or overexertion. There is a possible risk of physical injury such as risks associated with falls, including muscle or bone injury. A trained professional will lead the class in order to decrease the likelihood of this occurring. Also, we encourage all participants to monitor their own safety and inform the instructor if they have any concerns. Participants may have pain in their joints and sore muscles due to exercising. We do not expect anyone to feel severe pain, and any pain should go away in a few days. The class leader will encourage anyone feeling any pain to take a break or stop participating that day or to engage in a type of exercise that is less strenuous. Participants will also learn ways to exercise safely so that they do not experience any pain or stiffness, and they will learn how to treat pain safely at home.

MRI scans:

The MRI scans are performed with a powerful magnet, without using x-ray radiation or radioactive material. A specially designed computer converts information from the MRI scan into a visible image. The magnetism of the machine attracts certain metals, which could put participants at risk. Therefore, participants with pacemakers, infusion pumps, metallic-backed transdermal patches, metallic shrapnel, or any other metal in their body, will be excluded from the study. Participants may feel somewhat closed in (claustrophobic) during the MRI procedures. Also, the MRI scans will get quite noisy, and this may cause participants some discomfort, which can be aided through the provision of earplugs. Participants will be told of the potential discomfort of the scan and given a screening form to ensure they meet the physical requirements to participate.

D.2. Adequacy of Protection against Risk

D.2.1 Suicidal Risk

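### D.1.5 sends any truly unanticipated result, even one person's, through a genetic counselor and a letter to all subjects, although the study describes no genetic testing

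*Combined protocol and SAP*

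**What the plan says.** The rule is a single paragraph in D.1.5, placed before the part of that section headed for MRI scans. It applies when a truly unanticipated result appears and there is a compelling reason to inform subjects. Its scope is stated as "either for an individual or for a group".

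One procedure serves both cases:

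- **Who judges importance:** "Decisions regarding when something is of importance will be made by the study investigators in consultation with a genetic counselor".
- **What is done:** "we will submit a request to the University of Illinois IRB to send a letter to ALL subjects enrolled in the study".
- **What the letter offers:** "stating that information may be available with a phone number and have a trained person available to answer questions".
- **Costs:** "Study participants will not be responsible for the costs of genetic counseling incurred because of this study".

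The paragraph adds that the investigators do not expect any such results.

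Elsewhere, the protocol provides for brain imaging of individuals. C2.2 states: "Randomized participants of the intervention group will be invited to participate in optional MRI testing". The scans take place at Week 0 and Week 9, and C.4.2 excludes the wait-list group from them.

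**The concern.** Two parts of the rule do not suit this study.

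First, the adviser. A genetic counselor is the person to consult about genetic results, and this protocol describes no genetic component.

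Second, the route for an individual. If a result concerns one person, the described steps are a request to the IRB, then a letter to everybody, then apparently a telephone call made by whoever wants to know more. As described, the letter says only that information may be available. Nothing in it tells the affected person that the result is theirs.

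What is at stake is how a participant would learn of a result that matters to them. If staff followed the paragraph as written, that person would be told less directly than by a plain notification. The documents give no time for the IRB step, so no length of delay can be stated.

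**Working it through.** No arithmetic applies. The plan gives no figure on this point, and none is needed. The check is a comparison of sections.

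**1. Is this the only rule for unanticipated results?** In the supplied text, yes. The other escalation rules deal with different events:

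- C2.1: a PHQ score of 10 or higher in someone who declines to take part leads to a list of treatment facilities.
- C 6.8 and D.1.3: adverse events are evaluated, treated or referred, and followed.
- D.2.1 (Suicidal Risk): suicidal ideation at a visit leads to immediate notice to the principal investigator and clinician.
- D.3.1: danger to self or others leads to alerting the authorities.

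None of these covers a research result that turns out to matter.

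**2. Does the rule cover one person's result?** Yes, expressly, in the words "either for an individual or for a group". It gives no separate route for the individual case.

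**3. Is there a genetic component?** None is described. Genetics appears only in the two sentences of D.1.5 on the counselor and on counseling costs. D.1.2 lists interviews, evaluations, test results, task responses and questionnaires, with no genetic material. That list is weak evidence taken alone, because it also leaves out MR images. The absence of genetic sampling from the study procedures in sections C2 and C.6 is the stronger support.

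**4. Can the team reach one person without writing to all?** Yes. D.3.2 keeps names linked to subject numbers in a database open to the study team. C.5.2 plans telephone reminders and payments mailed to the participant's address. The all-subject letter is therefore not needed to reach the person concerned.

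**5. Could the rule reach an MRI finding?** Only on a literal reading. C.6.6 describes imaging of each scanned participant's brain, and nothing in the D.1.5 paragraph excludes a result from a scan. The MRI text in D.1.5 covers metal, claustrophobia and noise, and D.3.2 covers storage and access to images. Neither gives a disclosure route. No section says the scans are read for clinical findings, so the question arises only for something that happens to come to light.

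Steps 1 to 4 rest directly on the text. Step 5 is conditional.

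**The case against.** The strongest reply is that the paragraph is about genetic results and nothing else. Two of its sentences concern genetic counseling, it stands apart from the MRI text, and it looks like wording carried over from a genetic study. On that view it has nothing to act on here. It also requires both a truly unanticipated result and a compelling reason, says none is expected, and does not forbid direct contact. The MRI consent addendum mentioned in D.2.1 (Informed Consent) is a natural home for a procedure on individual findings. It is not in the supplied file, and its absence there is not a gap in the plan.

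Most of this stands, and it limits the point. A reader might infer that the plan deliberately sends incidental brain findings to a genetic counselor, or that it has no pathway for them. The documents support neither: the rule never names MRI, and the addendum cannot be seen. A reader might also measure harm by counting letters sent to people whom a result does not concern. That count says nothing about harm to the person whom it does concern, so no such share is offered.

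What the reply does not remove is the rule itself. The carry-over is an inference, but the paragraph is current text. It includes individual results in so many words, and the only procedure it prescribes is the indirect one. That no such result is expected is no defense of a rule written for unexpected results. A sound addendum would still leave the protocol with a different rule for individual results.

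**Conclusion.** Wrong as written, low severity. The named adviser does not fit a study that describes no genetic testing, and a letter to all subjects is a poor way to deliver one person's result when that person can be identified and contacted. Both conclusions come from the protocol's own text.

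The extension to MRI holds only under these conditions: something comes to light on a scan, it is judged truly unanticipated and compelling, staff take the D.1.5 paragraph as governing, and the addendum gives no pathway of its own. The documents do not show how likely that is, and no probability or delay is claimed.

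This is a matter of participant protection. Randomization, endpoints, sample size and analysis are untouched.

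**What to change.** In D.1.5:

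1. Delete the two sentences on the genetic counselor and genetic counseling costs.
2. For a result concerning one individual, have the investigators decide importance with a study physician, who refers to a suitable specialist as needed. Notify that person directly and promptly. The physician described in D.2.1 is a psychiatry clinician whose stated role there is suicidal risk, so referral onward should be written in and imaging expertise should not be assumed.
3. Keep the letter to all subjects, through the IRB, for group-level results only.
4. Check the MRI consent addendum first. If it already covers individual findings, cross-refer to it; otherwise make the two texts consistent.

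The cost is one IRB wording amendment to a single paragraph and one check against the addendum. No image reader or new procedure for reading scans is added.

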Recruitment will take place at the University of Illinois at Chicago campus, Oakwood Shores, clinics, churches, parks, free online community resources including Craigslist, and surrounding community areas. Recruitment will occur through advertisements about the study to individuals through printed brochures, flyers, news papers ads and announcements about the study. This will be followed by a telephone call where potential subjects can opt to go through the telephone or in-person screening process. The Resident Service Coordinator at Oakwood Shores will aid in the distribution of recruitment material and collection of names and numbers of potential

participants. The Resident Service Coordinator will not be responsible for conducting screenings or the collection of participant data, so will not be listed as authorized research personnel.

C.5.2 Attrition and Study Non-Completers/ Issue of Dropouts:

We estimate that 33% of subjects will not complete the protocol. While it would be optimal to have higher completion rate, this rate appears to represent the nature of the population. Subjects will also be financially compensated for each visit. Subjects will receive \$55 on via check delivered through the mail.. This payment will be in the form of a check and will be mailed to the participants' desired address. The following strategies for subject retention will be used: phone reminders/confirmation of visits, and established contact with the study coordinator. We will provide participants with a document that includes a list of scheduled appointments on the back. Based on these strategies, we anticipate that drop-out will be minimized to 33% of the sample.

C.6 Assessment of Subjects

C.6.1 Screening Measures (35 minutes)

Screening Form: This questionnaire asks respondents questions about medical and psychiatric history, related to the inclusion/exclusion criteria for this study. The screening form will be utilized prior to subject enrollment, either in person or over the phone, to determine if someone would be a good fit for participation in the study. (15 minutes)

MRI Screening Form: This questionnaire asks respondents questions about their medical history and willingness to participate in the MRI testing. The MRI screening will be given either over the phone, at the time of the general study screening, or in-person during the baseline visit (5 minutes).

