The clinician, [name] MD, PhD; Associate Professor; Associate Director, Residency Training and Education; Co-Director, Adult/Neuroscience Research Track; Department of Psychiatry, or research staff may remove a subject from the study if the clinical team thinks that the subject is at imminent suicidal risk, which, while not specifically assessed, may come up during the course of the study, given that individuals with significant depressive symptoms will be enrolled in the study. If the patient is deemed to have specific suicidal ideation during any of the visits, the PI and clinician will be immediately notified, and an appropriate clinical decision for emergent psychiatric evaluation will be made, including an evaluation of the need for hospitalization.. If the potential participant brings up suicidal ideation during the phone screen, they will be referred to the suicide prevention hotline.

D.2.1 Informed Consent

In most cases, potential subjects will learn basic information about the study during a telephone or in-person screening, and an informed consent will be mailed to those who are eligible for/interested in the study. At the time of initial contact with the study coordinator, subjects will be given detailed information about the study and the informed consent form will be reviewed and signed. Written consent from the participant will be obtained before the diagnostic interview begins. A copy of the document will be given to the study participant and the original informed consent document will be kept in a locked cabinet in the principal investigator's laboratory, separate from all other study materials. Other study materials (e.g., assessment measures) will be coded by an anonymous identification number. This identification number will be linked to the subject's name in an electronic database that can be accessed only by double password authentication. Participants will also be presented with an Informed Consent Addendum form addressing the MRI inclusion to the research study. They will be asked if they are willing to participate and will be informed of the additional compensation upon completion of each MRI

session. Participants will also be informed that refusal to participate in the MRI testing will have no effect on their participation in the research study.

D.3 Protections Against Risk

D.3.1 Protection Against Risk of Psychological and Social Discomfort

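### Suicidal ideation raised at the phone screen leads to a hotline referral but no stated notice to the PI or clinician, although the person may still be enrolled and wait-listed

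*Combined protocol and SAP*

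**What the plan says.** D.2.1 Suicidal Risk gives two responses to suicidal ideation, depending on where it arises.

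- At a visit: "If the patient is deemed to have specific suicidal ideation during any of the visits, the PI and clinician will be immediately notified", followed by a clinical decision on emergent evaluation, including whether hospitalization is needed.
- At the phone screen: "If the potential participant brings up suicidal ideation during the phone screen, they will be referred to the suicide prevention hotline". Nothing further is stated.

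The same section lets the clinician or research staff remove a subject who, in the clinical team's view, "is at imminent suicidal risk, which, while not specifically assessed, may come up during the course of the study".

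On the screen itself, C2.1 says: "Before being scheduled to a study visit, potential participants will undergo a phone or in-person screen". It goes on to say that those who want to take part have a screen described this way: "they will undergo a phone screen assessing past and current medical and psychiatric history". The PHQ-8 is given at the same contact. C2.1 has one other referral rule at this stage, for someone who "scores 10 or higher on the PHQ, but refuses to participate in the study, we will refer them to a list of treatment facilities". C.5.1 says that "potential subjects can opt to go through the telephone or in-person screening process", and C.6.1 says: "The screening form will be utilized prior to subject enrollment, either in person or over the phone".

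**The concern.** The screen asks about psychiatric history and depressive symptoms, and the study expects to enrol people with significant symptoms. Disclosure at screening is foreseeable, and the plan foresaw it by writing a phone-screen rule. That rule passes the person to an outside service and states no step that brings the information to the two people who make the clinical decision at visits.

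This would matter little if disclosure ended the person's contact with the study, but it need not. The next steps are a baseline visit, randomization and, for up to half of participants, a wait of about nine weeks before the next scheduled assessment. What is at stake is the safety of someone whose ideation is already known to study staff. The estimates and tests are unaffected.

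**Working it through.** No figure in the plan needs reproducing. The check sets the texts side by side and follows one person through them.

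**1. Stated response by contact**

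| Contact | Stated response to ideation | PI and clinician notice stated? |
|---|---|---|
| Phone screen | Hotline referral (D.2.1) | No |
| In-person screen | Not named in either D.2.1 rule | Depends on the reading |
| Study visit | Notice and decision on emergent evaluation (D.2.1) | Yes, immediate |

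**2. Does disclosure stop entry?** The inclusion criteria in C.4.1 require a PHQ-8 score of at least 1 and set no upper limit. The exclusions in C.4.2 cover medical and neurological illness, cognition, mobility, activity level and English proficiency. Ideation is not among them, so the person remains eligible.

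**3. Does other text supply the notice?**

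- D.3.1 item 2 makes the PI available, and tells the research assistant to contact the PI about problems, during study visits. C2.1 places the screen before a study visit is scheduled.
- D.3.1 item 3, on alerting authorities to danger, is also tied to the study visit.
- The treatment list in C2.1 is for people with a PHQ score of 10 or more who decline. Someone with that score who agrees to join has no stated referral under that rule.
- The removal power in D.2.1 concerns a subject in the study. It depends on the clinical team knowing of the risk and creates no duty to tell them.
- C 6.8 and D.1.3 send adverse events to the PI and provide for regular staff meetings on accrual, adverse events and data quality. Neither mentions disclosures at screening.

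**4. Would baseline catch it?** Possibly.

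- In favor: D.1.5 lists questions on history of suicidal behavior among those that subjects may find sensitive, and D.3.1 item 1 has the PI or a trained clinician conduct the clinical interview. A disclosure there triggers the visit rule.
- Against relying on it: D.2.1 says imminent risk is not specifically assessed; the only instrument listed under Clinical Interview in C.6.2 measures functioning; and C2.2 assigns the interview to a trained research assistant.

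**5. If baseline does not catch it.** C.1 assigns up to 20 of 40 people to the wait-list, 20/40 = 50%. Their classes begin at week 10, and C.1 has them complete all outcome measures before that. Hypothesis 2 sets the between-group comparison at 9 weeks, so the gap from baseline (week 0) to the next scheduled assessment is 9 − 0 = 9 weeks. People in the intervention arm attend classes three times a week and complete measures at weeks 4 and 8 (C2.3), so they have more contact.

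**6. Which rule covers an in-person screen?** Two readings are open. C2.1 introduces a screen by phone or in person and then calls it a phone screen, which suggests that the hotline rule covers both. The heading of C.2 divides contacts into the phone screen and study visits, which could put a face-to-face screen under the visit rule. The text does not settle it.

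**The case against.** The strongest defense is that the difference is deliberate. A caller has not consented and is not under the study's care. A hotline is an immediate, specific response, and it is reasonable to reserve the clinical pathway for people who attend. Every enrollee then has a baseline visit, where the fuller rule applies and where D.1.5 suggests the topic may be asked about. The screening form and script are also not reproduced in the protocol, so escalation steps may exist there.

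Much of this stands. The hotline referral is sound and should be kept. Baseline is a genuine second chance, so the unnoticed path needs both disclosure at screening and no detection at baseline. The finding is that notice is not stated in the protocol, not that it would fail to happen.

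The defense does not explain why information already in the study's hands should have to be found a second time. It also gives no help to a person who discloses and never reaches baseline.

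A reader might infer that someone screened in person has no rule at all. The documents do not support that: as shown above, either rule can be read to cover that screen, so the fault is ambiguity.

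**Conclusion.** The concern holds as a gap in the stated safety procedure. Ideation disclosed at the phone screen has a referral but no stated clinical review within the study, and the person can go on to enrolment and the wait-list. The rule for an in-person screen is ambiguous.

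Everyone screened is exposed to the weaker rule, including all 40 planned enrollees. The longest consequence is the nine-week interval for up to 20 wait-listed people. The documents give no rate of disclosure at screening or of detection at baseline, so no count of affected people is offered. A reader might infer that missed cases are likely in a sample of this size; nothing in the documents supports a probability either way.

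The conclusion assumes that the protocol text is the operative rule and that unseen screening materials add no notice step. If the script already requires one, only the wording of D.2.1 needs to be brought into line. The change is worth making because it is cheap and relies on people the plan already names.

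**What to change.** Replace the last sentence of D.2.1 Suicidal Risk with:

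> If suicidal ideation is disclosed at the phone or in-person screen, the person is referred to the suicide prevention hotline, and the PI and clinician are immediately notified and review the case before a baseline visit is scheduled.

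Add one line to the screening script telling the person that the PI and clinician will be informed, since consent has not yet been given. Naming both kinds of screen removes the ambiguity.

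**Cost.** A wording amendment with IRB review and a short briefing for screening staff. The PI or clinician must be reachable while screens are done, and scheduling of some baseline visits may be held briefly. Some people may disclose less once told who will be informed. No assessment is added, and the design and analysis do not change.
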